1. INTRODUCTION

Recurrent aphthosis is a disease with a multifactorial and immune-mediated inflammatory etiology. Clinically it is often associated with the manifestation of ulcers affecting the soft tissues and oral mucosa [1,2]. Recurrent aphthosis is epidemiologically the pathology of the oral district with the highest incidence around and occurs most frequently in subjects between 20 and 30 years of age [3,4].. The clinical course is often associated with periods of quiescence followed by phases of recrudescence and tends to occur less frequently and severely in the late phase of the adult subject [5,6]. In the case of an individual predisposition, this pathology can produce the appearance of recurrent lesions in adulthood, often also in association with systemic diseases or immunodepression [2,5,7]. The main individual and environmental predisposing factors are:

- Familiarity and heredity
- Microbiological factors
- Hypersensitivity
- Local traumas
- Hormonal disorders
- Immunological disorders
- States of stress and psychological disorders
- Smoking

An association with vitamin deficiencies (zinc, iron, vitamin B1, B2, B6, B12, folic acid) as well as gastrointestinal diseases, celiac disease and chronic inflammatory bowel diseases (Crohn's disease) is also reported in the literature [4,5,8,9]. In addition, recurrent aphthosis has been associated with Behcet's syndrome, Reiter's disease and AIDS. In addition, neutropenia and administration of beta-blockers, bisphosphonates, NSAIDs, protease inhibitors, sulfonamides are also predisposing factors [4–6,8–11].

In the literature, several protocols have been proposed for the treatment of recurrent aphthosis with symptomatic therapies and active ingredients such as chlorhexidine 0.2% in mouthwash, benzidamine, zinc chloride and polycresulene, where, however, many ulcerative lesions can sometimes recur and be refractory to such administrations [5,6,12–15]. Among the possible correlations to this failure is the effect of dilution and *Wash-out* of saliva. Bio-adhesion to oral tissues affected by canker sores is also a key factor in determining the effectiveness of the treatment [6,8–11].

2. PURPOSE OF THE RESEARCH

The aim of the present research is to evaluate the efficacy of a mouthwash formulation for a total treatment of 14 days for the treatment of oral ulcers of traumatic or aphthous nature.

The study groups are as follows:

- Group I (Test): Curasept Canker Sores Rapid Mouthwash: Dicaprylyl Ether, Coco-Caprylate/Caprate, Hydrolyzed RNA/DNA, Hyaluronic Acid, Cetyl Palmitate, Beta-Glucan.

Versus

- Group II (Control): Placebo mouthwash

Null hypothesis (H0): There is no difference at 14 days in the reduction of the mean pain sensation and ulcer area score, thermography [16,17] and Ulcer Severity Score (USS) [18] in the two groups, against the alternative hypothesis of a difference between them.

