3. STUDY DESIGN

The present study is a 2-week double-arm randomized controlled trial.

The study will be carried out in the following ways:

- Randomization: Using a computer-generated, centralized random number with random codes (A, B) placed in sequentially numbered sealed opaque envelopes provided by the study consultant. A simple randomization procedure will be used.
- Concealment of assignment: Doctors involved in patient treatment will never know which mouthwash will be delivered to patients. Identical and indistinguishable bottles with mouthwash will be prepared by a person designated by the sponsor. The mouthwash will be poured into identical vials labeled with only one letter (A, B), and only the person designated by the sponsor will be of which product matches the letters. The random assignment will be made by opening the sequentially numbered sealed envelope just before the surgery.
- Blinded assessment: A single, independent, blinded assessor will perform all clinical measurements. Patients will not be aware of the mouthwash they will use. In addition, the operator evaluators and statistician will remain blinded until statistical analysis (blinded study) is performed. The codices (A, B) will be broken at the time of writing the manuscript.

The principles outlined in the Declaration of Helsinki on clinical research involving human subjects will be respected. Written informed consent will be obtained for each patient.

The study will be reported according to the CONSORT statement to improve the quality of reports of randomized parallel-group trials (<http://www.consort-statement.org/>).

A total of 3 visits will therefore be carried out:

- A screening/baseline visit will help establish patients' eligibility for inclusion in the study, followed by baseline data recording and first supervised mouthwash application
- A 1-week experimental visit
- A 2-week experimental visit and end of study

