3. CRITERIA FOR THE SELECTION OF STUDY SUBJECTS

3.1 Inclusion Criteria

Patients must meet all of the following inclusion criteria to be eligible for study enrollment:

1. Patients with at least one well-defined ulcer
2. Any patient who is at least 18 years old and able to sign an informed consent.

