4.4 Study program

Screening and baseline visit (V1)

Potentially eligible patients are screened to determine their eligibility for the study. Complete (Patient Eligibility CRF) and record the number and reason for patients not included.

Prior to enrollment, all patients will be asked to sign an informed consent form to document that they understand the purpose of the study (including procedures, follow-up assessments, and any potential risks involved), have been given the opportunity to ask questions related to this study, and have been informed of treatment alternatives.

At the recruitment visit, the clinician should assess the presence of an oral ulcer, rule out lesions of neoplastic, infectious, or allergic origin, and remove, if present, any causative agents (such as sharp edges of teeth, fillings, crowns, dentures, or braces).

Primary Results:

- Pain intensity. It is measured using the VAS consisting of a 10 cm line [13], where 0 indicates no pain and 10 indicates severe pain.
- Size of each ulcer. A sheet of clear plastic will be applied directly to the ulcer and using a permanent waterproof marker the circumference of the ulcer will be traced and then placed on a graph paper and the number of mm² units included within the drawn area will be counted.

Secondary Results:

- Thermography
- Ulcer Severity Score (USS)

Treatment will be started on the same day with strict infection control measures.

The assessor will open the sequentially sealed envelope corresponding to the patient's recruitment number and write on the CRF the progressive number of the patient contained in the envelope and to which group (A or B) the patient will be assigned.

Patients will receive three anonymous bottles, coded with A, B containing the mouthwash and a scoop. Patients will apply mouthwash. This procedure will be performed under the supervision of the outcome measure which will provide further explanations to patients if necessary.

Participants will be asked to flush with 10mL of mouthwash twice daily ~~directly onto the ulcer~~. Patients were prevented from eating, drinking, or rinsing their mouths for at least one hour after each application.

Observation at 1 week (V2) and at 2 weeks (V3):

- Pain intensity using the VAS scale. The following outcome measures will be recorded by the blinded outcome assessor:
- Size of each ulcer using a clear plastic sheet
- Thermography/ Ulcer severity score (USS)

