7.3 Statistical analysis

Descriptive statistics will be provided in summary tables by group based on the type of outcome measure summarized.

General descriptive statistics for continuous outcome measures will include n (number of observed values), mean with its 95% CI, standard deviation, median, minimum and maximum values. For categorical variables, the number and percentage of subjects with a specific level of the variable will be presented.

This primary efficacy analysis will be performed on ITT, using the null hypothesis of no between-group difference in overall VAS change from baseline between both groups:

$$H_0: \mu_{\text{AfteRapidDNA}} = \mu_{\text{Placebo}}$$

$$H_1: \mu_{\text{AfteRapidDNA}} \neq \mu_{\text{Placebo}}$$

Where μ is the mean change from baseline on Day 7 within the given product.

This hypothesis will be tested with an Analysis of Variance (ANOVA) with baseline values of VAS as a covariate. The groups will be compared to the bilateral significance level of 5%.

The assumption of normality will be verified by means of QQ graphs and by plotting the studentized residuals with respect to the expected values of the variable. If there are strong indications of non-normality of the data, the Wilcoxon Rank-Sum Test will be used to test the hypothesis of no median difference between buccacollutorio and placebo at Day 7 in a nonparametric manner. Summaries for each treatment group will include sample size, mean, median, standard deviation, minimum, maximum, Wilcoxon Rank-Sum test p-value, Hodges-Lehman point estimates of median treatment difference, and its 95% confidence interval.

From the Day 7 endpoint ANOVA model, a least squares estimate (LSMEANS) of the group effect and group difference (both with 95% confidence intervals) will be displayed along with the p-value of the difference between the groups.

Analysis will also be performed for the PP Analysis Set to test the robustness of the results.

For secondary quantitative efficacy variables, cross-treatment group comparison of change from baseline will be done by the same ANOVA model used in the primary efficacy analysis. Categorical derived variables (complications/adverse events) will be compared via a chi-square test or Fisher's exact test, as appropriate (chi-square test will be used if all groups have sufficient observations,

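### Traumatic and aphthous ulcers are pooled with no stratification or model term for ulcer type, which leaves avoidable chance imbalance and some lost precision in the efficacy comparisons

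*Combined protocol and SAP*

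**What the plan says.** All references are to the combined protocol and SAP.

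- **Population.** Section 2 gives the aim as efficacy of the mouthwash "for the treatment of oral ulcers of traumatic or aphthous nature". Section 3.1 admits adults under a single lesion criterion, "Patients with at least one well-defined ulcer", so either type qualifies.
- **Baseline procedure.** In section 4.4 the clinician confirms an ulcer, excludes neoplastic, infectious and allergic lesions, and must "remove, if present, any causative agents (such as sharp edges of teeth, fillings, crowns, dentures, or braces". This applies to every patient and is described before the envelope step.
- **Allocation.** Section 3 (Study design): "A simple randomization procedure will be used". No strata or blocks are mentioned.
- **Model.** Section 7.3 tests the Day 7 VAS change with an "Analysis of Variance (ANOVA) with baseline values of VAS as a covariate". The comparison of quantitative secondary variables "will be done by the same ANOVA model used in the primary efficacy analysis". Ulcer area is listed as primary in section 6.1 but gets no model of its own in section 7.3; I take it to be analysed in the same way.

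Ulcer type does not appear in the visit flowchart, the list of CRFs in section 8, or the analysis section.

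**The concern.** Some patients will have a mechanical cause taken away on Day 0 and others will have nothing to take away. The primary comparison falls one week later, so the two kinds of patient could well improve at different rates in either arm. Baseline VAS can absorb a difference in starting pain, but not a difference in healing course. The USS items on average lesion duration and ulcer-free period (section 6.2) describe recurrent disease and fit an isolated traumatic ulcer poorly, so that score may also differ by type.

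A baseline factor that predicts outcome, is neither balanced nor modelled, and may not be recorded has two consequences in a trial of 60. The arms can differ in mix by chance and move the estimate in that one trial, and the spread between types stays in the error term. The introduction argues from recurrent aphthosis alone, yet without a recorded type the results in those patients cannot be described separately.

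**Working it through.** **Inputs from the documents.** 30 per arm, 60 in total; difference 0.820; SD 1.80; two-group t test at 5%; 80% power (section 7.1). Section 7.1 does not name the endpoint; I read 0.820 and 1.80 as VAS points.

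**Inputs assumed.** Share of traumatic ulcers p = 0.3 to 0.5. Difference between types in mean VAS change g = 0.9 to 1.8 points (half to one SD), with 1.0 and 2.0 used in the power check. The documents give neither p nor g.

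**Step 1, the plan's own figure.** n per group = 2 × (1.960 + 0.842)² × 1.80² / 0.82² = 75.6, so 76 (77 with the exact t test). The stated 29 is not reproduced; power with 30 per group is about 41%. This is a separate problem, shown because it sets the baseline for the power figures in step 5.

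**Step 2, chance imbalance.** With about 30 per arm, the SD of the between-arm difference in traumatic share is roughly √[p(1−p) × 2/30]. That is 0.118 at p = 0.3 and 0.129 at p = 0.5. Simulating simple randomisation of 60 patients, which also lets arm sizes vary, gives:

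| p | SD of difference | P(gap ≥ 10 percentage points) | P(gap ≥ 20 percentage points) |
|---|---|---|---|
| 0.3 | 0.119 | 40% | 10% |
| 0.5 | 0.130 | 44% | 13% |

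**Step 3, shift in the estimate.** A 20-point gap moves the unadjusted VAS difference by 0.20 × g.

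- g = 0.9: 0.18, which is 0.18/0.82 = 22% of the target.
- g = 1.8: 0.36, which is 0.36/0.82 = 44% of the target.

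For scale, the standard error of the difference is 1.80 × √(2/30) = 0.46, so even the larger shift is below one standard error.

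**Step 4, variance explained.** If 1.80 is the within-type SD, R² = p(1−p)g² / [1.80² + p(1−p)g²].

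- g = 0.9: 0.170/3.410 = 5% at p = 0.3; 0.2025/3.4425 = 6% at p = 0.5.
- g = 1.8: 0.680/3.920 = 17% at p = 0.3; 0.81/4.05 = 20% at p = 0.5.

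**Step 5, error rate and power.** Simulated trials of 60 with p = 0.5, within-type SD 1.80, true difference 0.82 for power, and no baseline VAS term:

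| g | Type I error, without / with type in model | Power, without / with type in model |
|---|---|---|
| 1 | 5.0% / 4.9% | 38.7% / 40.4% |
| 2 | 4.8% / 4.7% | 32.5% / 40.2% |

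**Step 6, does stratifying alone help?** With 30 patients of each type and coin-flip allocation inside each type, the SD of the difference in traumatic share is 0.131, and a gap of 20 points or more still occurs in about 15-16% of trials. Strata without blocks do not reduce the imbalance.

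**The case against.** The strongest reply is that this is an optional precision covariate. Randomisation protects the comparison, type I error is unaffected, and the gain is small unless the types differ a great deal. That stands: at a type difference of 1 point the power gain is under two percentage points. The 44% figure needs both a one-SD difference between types and an imbalance seen in at most about 13% of trials. Baseline VAS, already in the model, may absorb part of any type effect. If 1.80 already describes the mixed population, the extra spread is in the plan's SD, although adjusting would still reduce it.

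Three stronger readings are tempting, and the documents do not support them.

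- **That removing the cause confounds the product effect.** Removal is done in both arms and is described before allocation, so it does not by itself favour either arm. The stated aim is the pooled indication, and a main-effect term for type would not give an aphthous-specific treatment effect.
- **That ulcer type is already established before randomisation and divides patients cleanly.** Section 4.4 asks for no traumatic/aphthous label, and the introduction lists local trauma among the factors predisposing to aphthosis. An aphthous patient may also have a sharp edge removed, so some misclassification is to be expected.
- **That every outcome is affected.** The point covers VAS, ulcer area, thermography and USS. Nothing in the documents ties complications or adverse events to ulcer type.

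**Conclusion.** The point holds as a matter of precision and chance imbalance in the four efficacy outcomes. The pooling, the removal of causes on Day 0, the simple randomisation and the single covariate are all in the text. That type predicts the Day 7 change is a plausible inference from the protocol's own procedure, not a documented fact.

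The size rests on assumed values of p and g. It is minor if the types differ by about 1 VAS point or less, and material only as the difference approaches 2 points, where modelling type recovers roughly 8 percentage points of power (32.5% to 40.2%). The change is worth making because it is cheap and because an unrecorded type may not be recoverable later. It does not repair the sample size.

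**What to change.** 1. Add an item to the V1 CRF, completed before the envelope is opened: ulcer type (traumatic or aphthous) or, where type is uncertain, whether a causative agent was removed (yes/no). State in advance which variable enters the model and how uncertain ulcers are coded.
2. Prespecify that variable as a fixed factor, alongside the baseline value, in the models for VAS, ulcer area, thermography and USS.
3. Report treatment effects by type descriptively, with confidence intervals and no claim from either subgroup.
4. If randomisation has not started, the list may also be stratified by this variable, but only with blocks within each stratum.

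**Cost.** One CRF item, one degree of freedom, some misclassification of uncertain ulcers and, if stratified, a second series of envelopes. If recruitment has begun, steps 1 to 3 still work for patients whose type was recorded or can be recovered from baseline records without knowledge of allocation.

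### The pain hypothesis is stated at 14 days, but the only analysis labelled primary tests pain at Day 7, and pain at Day 14 has no explicitly assigned test

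*Combined protocol and SAP*

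**What the plan says.** Section 2 (Purpose of the research) describes a 14-day treatment and gives the null hypothesis as "There is no difference at 14 days in the reduction of the mean pain sensation and ulcer area score", with thermography and USS under the same statement. Section 3 (Study design) places the last assessment at that point: "A 2-week experimental visit and end of study".

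Section 7.3 (Statistical analysis) introduces one primary efficacy analysis, on the ITT population, "using the null hypothesis of no between-group difference in overall VAS change from baseline between both groups". It writes out H0 and H1 and then says that μ "is the mean change from baseline on Day 7 within the given product". If normality fails, the replacement test addresses "no median difference between buccacollutorio and placebo at Day 7". The reported estimates come "From the Day 7 endpoint ANOVA model, a least squares estimate (LSMEANS) of the group effect".

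The only other efficacy rule in section 7.3 reads: "For secondary quantitative efficacy variables, cross-treatment group comparison of change from baseline will be done by the same ANOVA model". It names no visit.

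Sections 4.4 and 6.1 list pain (VAS) and ulcer size as the primary results. Sections 4.4 and 6.2 list thermography and USS as the secondary ones. The flowchart and section 6.1.1 schedule VAS at baseline, Day 7 and Day 14.

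**The concern.** A trial's stated hypothesis and its primary test should concern the same quantity. Here they concern the same outcome at different visits: end of treatment in section 2 and mid-treatment in section 7.3. A between-group difference in pain change at one week is not the same estimand as one at two weeks, and a result at one day does not answer a hypothesis about the other.

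If the analysis is run exactly as section 7.3 directs, the report will contain a test of Day 7 pain. The 14-day pain hypothesis, which section 2 presents as what the trial sets out to examine, will have no test that the plan assigns to it. Day 14 VAS will have been collected, but its analysis would have to be decided outside the plan.

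**Working it through.** No arithmetic applies. The check is to set every statement that could fix the day for pain side by side.

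| Place | Outcome | Day named |
|---|---|---|
| Section 2, null hypothesis | Pain, ulcer area, thermography, USS | 14 days |
| Section 7.1, sample size | None named | None |
| Section 7.2, per-protocol rule | Primary outcome measures, not listed | None |
| Section 7.3, opening of the primary analysis | VAS change, called *overall* | None in that sentence |
| Section 7.3, definition of μ | VAS change | Day 7 |
| Section 7.3, Wilcoxon fallback | Primary comparison | Day 7 |
| Section 7.3, least squares means | Primary model | Day 7 |
| Section 7.3, secondary variables | Secondary quantitative variables | None |

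**Step 1: which day does the primary test use?** Day 7. The definition of μ belongs to the same hypothesis statement as the word *overall* and fixes it. The fallback and the model output agree. Across sections 7.1 to 7.3, Day 7 appears three times and Day 14, in any wording, not at all.

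**Step 2: does anything reconcile this with section 2?** No. Section 2 names only 14 days, section 7.3 names only Day 7, and no sentence ranks one over the other. Section 7.1 cannot decide the matter, because it names neither an outcome nor a visit for its difference and standard deviation.

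**Step 3: is Day 14 VAS tested elsewhere?** The only candidate is the sentence on secondary variables. It can be read in two ways:

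- If *same ANOVA model* carries the Day 7 time point with it, thermography and USS are also tested at Day 7, and no part of the 14-day hypothesis is expressly tested.
- If it carries only the model form, the day for those variables is undefined.

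On either reading the sentence covers secondary variables, and VAS is not listed as one. Day 14 VAS is therefore collected without an explicitly assigned test.

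**Step 4: does the gap go beyond VAS?** Yes. Ulcer area is the other listed primary result and falls under the same 14-day hypothesis. The primary analysis covers VAS only and the secondary sentence covers secondary variables only, so ulcer area has no explicitly assigned test or day either.

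**Step 5: the per-protocol set.** Membership requires the primary outcome measures to be present, but at no stated day. Whether a patient with a Day 7 VAS and no Day 14 VAS belongs is undefined. This touches only the robustness analysis.

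**The case against.** The strongest reply is that section 7.3 is the operative text. It gives formal hypotheses, defines the parameter and repeats the day, so Day 7 is primary and section 2 is a general statement of purpose. Half of this stands. Section 7.3 does fix its own test at Day 7, and *overall* is loose wording rather than a second time point. But section 2 states a formal null hypothesis with a day attached, and nothing demotes it. If section 7.3 governs, the section 2 pain hypothesis is left without a test, which is the defect.

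A second reply is that Day 14 VAS can be treated as a secondary variable under the same model. That would be a sensible intention, but the documents class VAS as primary and the sentence names no visit, so it has to be inferred.

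A reader might also infer more than the documents support:

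- *That the false-positive rate is inflated by two chances at pain.* The plan has no rule under which success on either day counts. One test is labelled primary, at a two-sided 5% level.
- *That the day will be chosen after coded results are seen*, since "The codices (A, B) will be broken at the time of writing the manuscript". The plan describes no such step. Late code-breaking, with the statistician blinded until the analysis is done, is a safeguard and not evidence of selection.
- *That other sections show which day was meant.* The data management text on sending CRF copies after the 1-week follow-up concerns paperwork and sets no precedence. The sample-size inputs are tied to no visit.

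**Conclusion.** The point holds and should be corrected before any between-group comparison. Sections 2 and 7.3 give different days for pain, no precedence is stated, and VAS at Day 14 has no explicitly assigned test. Followed exactly, the plan tests a different pain hypothesis from the one it declares.

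The size is a matter of definition and not of error rates: the primary question is placed at two visits, and the analysis section serves only one of them. No loss of power or change in significance level is claimed.

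The conclusion rests on two readings of the text: that the null hypothesis in section 2 is meant as the trial's hypothesis, and that VAS is primary and not secondary, as sections 4.4 and 6.1 list it. It does not depend on which day the sponsor intended, and the documents do not settle that.

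**What to change.** Before any comparison between groups, including by coded arm A versus B, the sponsor should:

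1. Name one primary time point for VAS and use it in both section 2 and section 7.3, replacing *overall* with that day.
2. Make VAS at the other day a named secondary outcome, analysed with the same baseline-adjusted model.
3. If Day 7 is kept for VAS, reword section 2 so that pain is separated from the outcomes hypothesised at 14 days.
4. Give ulcer area a stated day and the same model, and state the day in the sentence on secondary variables.
5. State in section 7.2 the day at which primary outcome measures must be present for the per-protocol set.
6. State in section 7.1 which outcome and day its difference and standard deviation refer to.

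The cost is protocol and SAP wording. VAS, ulcer size, thermography and USS are already scheduled at Day 7 and Day 14, so no new data or visits are needed.
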